3.4 Patient-Reported Outcomes and Provider Assessment Tools for Radiation Dermatitis

Currently, the most widely used standardized method of recording provider-assessed toxicities is the CTCAE version 4. CTCAE has been shown to result in stable assessments of toxicities among practitioners (Trotti, 2003). Using this assessment tool, grade ≥ 2 radiation dermatitis encompasses an assessment of both the degree of erythema and desquamation, as gauged by the provider. Grade 2 erythema is defined as “moderate to brisk,” and grade 2 MD is defined as “patchy, mostly confined to skin folds and creases” (CTCAE v4.03, 2009).

There is evidence that patients and clinicians differ in their assessment of the severity of subjective skin toxicities (such as pruritus) during radiation (Neben-Wittich M. A., 2011). The Skindex-16 is a tool designed to capture patient-reported assessments of subjective adverse effects. Skindex-16 is comprised of sixteen questions, which are sub-categorized into an emotional subscale (six questions), a functional subscale (five questions), and a symptom subscale (five questions). Rankings of the questionnaire are then averaged to obtain a score of severity of patient-reported outcomes. This allows providers to gauge which aspects of the patient’s experience are most affected by the treatment.

The Fitzpatrick Skin Classification is a well-recognized tool for patients’ initial assessment of their general level of skin sensitivity. The scale ranges from category I to VI, representing a range from pale skin/always burns to dark skin/never burns (Fitzpatrick TB, 1988).

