8.0 PRETREATMENT EVALUATION

The History and physical exam in Radiation Oncology will include information on race/ethnicity, age, body mass index, chemotherapy status, hormone therapy, smoking history/status, diabetes, high blood pressure, Eastern Cooperative Oncology Group (ECOG) performance, and reconstruction status.

Radiation Treatment Planning will be approved by the treating MD, in order to determine type of chest wall radiotherapy (photons vs electrons) to be administered, as outlined in section 9.1.

Baseline Provider Skin Toxicity Assessment will be done within 14 days prior to the start of RT.

Patients will complete a baseline Skindex-16 Questionnaire and Fitzpatrick Skin Classification within 14 days prior to the start of RT (Appendix 1 and 2).

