9.0 TREATMENT/INTERVENTION PLAN

9.1 Skin Cream Application

Arm 1 consists of patients randomized to standard of care arm (Eucerin) and Arm 2 is the experimental arm (MF 0.1%). Patients will start applying the agent to the chest wall twice daily beginning on the first day of radiation treatment and continuing 10-14 days post-completion of RT.

Patient education regarding amount to be applied (amount depending on body habitus) and area of treatment field will be reinforced by the R.N. prior to the first radiation treatment. Patients will be instructed to apply cream to the upper outer quadrant, upper inner quadrant, lower outer quadrant, and lower inner quadrant, as well as irradiated nodal fields. They will be instructed to apply cream in a thin, uniform layer twice a day, in the morning and evening, and not within the immediate 4 hours prior to radiation treatment. Patients will be informed that application immediately following radiation treatment is acceptable for those scheduled to receive morning treatments.

Patients will be instructed to wash the area daily using a mild soap such as Dove or Cetaphil, and to pat skin dry prior to cream application. Patients will be instructed to avoid the use of any exfoliating agents, such as loofah, sponges, or scrubs. Skin will not be washed for at least 8 hours after each application.

Patients will be instructed to wear soft, loose clothing to cover the treated areas, but not to use any occlusive dressings, and to avoid exposure to the sun. The use of sunscreens should be discouraged, with a preference to using clothing to cover the treatment area when exposure to the sun is expected. Patients will be discouraged from scratching the treated area and using possible skin irritants such as aftershaves, colognes, and perfumes. Aluminum-free deodorants will be permitted. Topical and/or systemic treatments for prophylaxis of dermatitis other than assigned cream will be prohibited during the study.

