12.2 Assessment of Secondary Objectives

The Skindex-16 module score will be utilized to assess patient-reported toxicities at baseline, during week 5 of RT, and 10-14 days post-RT.

The maximal reported toxicity score and time to occurrence will be assessed weekly and at the two week follow up.

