14.0 BIOSTATISTICS

This is a double-blinded, randomized trial (see Section 15.2 for details of randomization) to compare MF 0.1% cream with standard skin care (Eucerin) on the prevention of moderate to severe skin toxicities in breast cancer patients receiving post-mastectomy radiation to the chest wall and regional lymph nodes. A patient is deemed to have developed skin toxicity if she has a grade ≥ 2 skin toxicity as defined in Section 3.4 within 7 weeks from the beginning of radiation.

Based on estimates provided by radiation oncologists at our institution, the rate of grade ≥ 2 toxicity using Eucerin as skin care for chest wall radiation is $\approx 50\%$. This estimate is slightly lower than the findings from the Spierer study cited in section 3.2, to reflect this study's inclusion of patients treated with photons (in the presence of reconstruction) as well as electrons. We expect that the usage of MF can reduce this rate to 25%. 124 evaluable patients are needed for the comparison, with 62 patients in each arm. Two-sample, two-sided proportion tests will be used to derive the statistical significance. One interim analysis will be conducted when 31 patients in each arm have been enrolled and evaluated using the O'Brien-Flemming procedure, which will declare significance if the test p-value is less than 0.005. Correspondingly the final analysis will declare significance if the test p-value is less than 0.048. This design has a power of approximately 0.83 (i.e., detecting the true toxicity rate of 25% or lower) at the type I error (i.e., declaring MF more effective while it yields the same toxicity rate as Eucerin) rate of 0.05 based on 100000 statistical simulations.

All deaths unrelated to the toxicities, and patients lost to follow-up (before toxicities can be evaluated), will be excluded from the comparison and new patients will be accrued for replacement. To this end we plan to enroll an additional 15% of patients. Therefore our final proposed accrual is about 143 patients, which is expected to be done in 3 years.

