Patient-reported skin symptoms will be scored from the Skindex-16 surveys and compared between interventions using Wilcoxon tests at each separate assessment time point. Analysis of covariance may also be used when the baseline information is taken into account as a covariate. Multiple comparison tools will be employed to adjust for statistical significance levels. Maximum reported skin toxicities will be tabulated and summary statistics will be provided. Time to occurrence of skin toxicity will be handled by routine survival analysis such as Kaplan-Meier estimation, log-rank tests, and/or Cox regression models when comparisons are needed.

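### Baseline adjustment of Skindex-16 is left optional; a specified rank-based ANCOVA would be a cheap, modest precision gain on a secondary endpoint

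*Combined protocol and SAP*

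**What the plan says.** Section 2.0 lists the comparison of patient-reported skin symptoms first among the secondary objectives. Section 14.0 gives its analysis in three sentences. Skindex-16 scores will be "compared between interventions using Wilcoxon tests at each separate assessment time point". Next, "Analysis of covariance may also be used when the baseline information is taken into account as a covariate". Then, "Multiple comparison tools will be employed to adjust for statistical significance levels".

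The material for an adjusted analysis is already collected:

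- Section 8.0: "Patients will complete a baseline Skindex-16 Questionnaire", in the 14 days before radiation starts.
- Section 9.1: cream is applied "twice daily beginning on the first day of radiation treatment", so the baseline score comes before any exposure.
- Section 12.2: the module score is used to "assess patient-reported toxicities at baseline, during week 5 of RT, and 10-14 days post-RT", so two of the three time points are post-baseline.
- Sections 1.0 and 15.2: randomisation is stratified by reconstruction (yes or no) and BMI (below 30, or 30 and above). No analysis in section 14.0 uses these factors.

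**The concern.** The plan commits to a test that looks only at follow-up scores. A score measured before treatment can remove between-patient variation from the comparison, and here it is a proper covariate. The table in section 10.2 places both randomisation and the baseline questionnaire at simulation, but the trial is double-blind and cream use starts later, so treatment cannot have affected the score.

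The ANCOVA that could use it has no model, no trigger and no status relative to the Wilcoxon test. The test that carries the conclusion therefore gains nothing from the baseline data. What is at stake is precision on the trial's only patient-reported outcome. Bias is not at issue, and neither is the primary comparison.

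**Working it through.** **The plan's own figure.** The only design calculation in section 14.0 is for the primary endpoint: 62 per arm, 50% v 25%, power about 0.83. It reproduces: 0.828 for a fixed-sample two-sided test at 0.05, and 0.835 by simulating the two looks (p<0.005 at 31 per arm, p<0.048 at 62). It is not disputed. It supplies the 62 per arm used below.

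**Inputs.** From the documents: 62 per arm, 1:1 allocation, items scored 0 to 6 (section 5.3), two binary strata. Assumed, because the documents give none: baseline-to-follow-up correlation rho, a shift of 0.503 SD, 10% missing baselines (20% also tried), and the score distribution. All power figures are at two-sided 0.05.

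**Formula check (normal scores, complete baselines).** The shift that gives an unadjusted normal-theory test 80% power is (1.960 + 0.842) × √(2/62) = 0.503 SD.

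- Wilcoxon has relative efficiency 3/π = 0.955, equivalent to 62 × 0.955 = 59.2 per arm. Power is 0.782 at any rho.
- Ordinary ANCOVA multiplies the variance by 1 − rho². At rho 0.3 this is 0.91, equivalent to 62/0.91 = 68.1 per arm, power 0.836. At rho 0.5 it is 0.75, equivalent to 62/0.75 = 82.7 per arm, power 0.899.

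These ANCOVA figures are favourable to adjustment. On skewed 0–6 scores with many zeros (59% at baseline, 23% at follow-up in the control arm), ordinary ANCOVA has power 0.646, 0.677 and 0.727 at rho 0, 0.3 and 0.5, against about 0.75 for Wilcoxon. The useful comparison is therefore with a rank-based ANCOVA.

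**Simulation of rank ANCOVA.** Follow-up rank is regressed on arm, baseline rank and the two strata. A missing baseline gets the pooled mean rank. There are 10,000 replicates per cell, with 10% of baselines missing at random. In the skewed case rho is the latent value; the observed correlations are about 0, 0.22 and 0.39.

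| Scores | Rho | Rank ANCOVA | Wilcoxon | Change |
|---|---|---|---|---|
| Normal | 0 | 0.767 | 0.781 | −0.014 |
| Normal | 0.3 | 0.789 | 0.766 | +0.023 |
| Normal | 0.5 | 0.851 | 0.774 | +0.077 |
| Skewed | 0 | 0.734 | 0.746 | −0.012 |
| Skewed | 0.3 | 0.763 | 0.747 | +0.016 |
| Skewed | 0.5 | 0.803 | 0.745 | +0.058 |

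The simulation error of one power figure is about √(0.75 × 0.25/10,000) = 0.004, so differences of 0.01 are small against noise. Type I error of the rank ANCOVA over all null cells was 0.045 to 0.054. With 20% missing, the changes are about −0.01, +0.01 to +0.02, and +0.05 to +0.07.

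**Floor effect.** Section 6.2 excludes patients with more than grade 1 skin toxicity, cellulitis or unhealed wounds at the application site, so baseline scores may cluster at zero more heavily than 59%. Varying the share of zeros (6,000 runs per cell) gave:

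| Zeros at baseline | Rho 0 | Rho 0.3 | Rho 0.5 |
|---|---|---|---|
| 59% | −0.01 | +0.01 | +0.06 |
| 75% | 0.00 | +0.01 | +0.04 |
| 85% | −0.01 | 0.00 | +0.03 |

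**Missing baselines.** If patients without a baseline are dropped, rank ANCOVA with 10% missing has power 0.720 and 0.746 (normal) and 0.689 and 0.715 (skewed) at rho 0 and 0.3. That is 0.02 to 0.06 below Wilcoxon, so the rule for missing baselines has to be part of the fix.

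**Strata.** The simulations gave reconstruction and BMI no prognostic effect, so they say nothing about any gain from them.

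**The case against.** The strongest reply is that nothing here is an error. A distribution-free test is a sound choice for a bounded, probably skewed score, and the figures above bear out that caution: ordinary ANCOVA does worse than Wilcoxon on skewed data at rho 0.5 or below. The plan also provides for baseline adjustment, if only as an option. The gain rests on assumed inputs, nearly vanishes at rho 0.3 or below, and about halves at rho 0.5 when 85% of baselines are zero. All of that stands, and it is why the point is low priority. It does not answer the narrower point: an optional ANCOVA without a role adds no precision to the test that governs, and a rank version risks about 0.01 power at worst for a possible gain of several points.

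A reader might infer three stronger things that the documents do not support.

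- *The plan ignores baseline, or its test is invalid.* ANCOVA is named, and Wilcoxon kept its type I error near 5% in simulation.
- *Two candidate tests inflate the error rate.* The wording commits to Wilcoxon and presents ANCOVA as an addition, and a multiplicity adjustment is promised. Always reporting the better of Wilcoxon and ordinary ANCOVA would give 0.06 to 0.08 per unadjusted comparison, but that is an upper bound on a practice that the plan does not describe. It is 0.03 to 0.04 if the adjustment covers both tests.
- *Leaving out the strata costs a known amount of power.* Section 14.0 lowers its assumed control toxicity rate because reconstructed, photon-treated patients are included, which suggests that reconstruction matters for provider-graded toxicity. Nothing links either factor to Skindex-16.

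**Conclusion.** The concern holds as a precision point on a secondary endpoint. With 62 per arm, a 0.5 SD shift, 10% missing baselines and two-sided 0.05, replacing Wilcoxon by the specified rank ANCOVA changes power by about −0.01 at rho 0, 0 to +0.02 at rho 0.3, and +0.03 to +0.08 at rho 0.5. The low end belongs to baselines that are 75–85% zeros. Every one of these inputs except the sample size is an assumption. Any gain from reconstruction and BMI would come on top if they predict Skindex-16, but its size is unknown. It would be wrong to take the 0.90 power from the normal-theory formula at rho 0.5 as the expected benefit, since that needs normal scores and complete baselines. The validity of the planned test, the primary endpoint and the sample size are not in question.

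**What to change.** Before unblinding, amend section 14.0 as follows.

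- Name one governing Skindex-16 analysis at week 5 and at the visit 10–14 days after radiation: rank follow-up and baseline scores over both arms pooled, then regress follow-up rank on arm, baseline rank, reconstruction and BMI stratum.
- Give a missing baseline the pooled mean rank, so that no patient with a follow-up score is dropped.
- Keep the Wilcoxon test as a sensitivity analysis.
- Report unadjusted summaries by arm beside the test.
- Describe baseline scores by arm without testing them; read literally, the present wording on time points would include such a test.

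The cost is wording only, since all the data are already collected. There are two downsides: about 0.01 power is lost if rho is near 0, and the adjusted estimate is on a rank scale, which is why the unadjusted summaries are needed.

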2.0 OBJECTIVES AND SCIENTIFIC AIMS

Primary Objective

- To determine if MF, as compared to Eucerin, is effective in preventing grade 2 or higher radiation dermatitis, particularly moist desquamation and/or moderate to brisk erythema in women receiving PMRT

Secondary Objectives

- To compare patient-reported skin symptoms between interventions
- To determine maximum reported skin toxicity and the time to occurrence

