Factors contributing to variation in the severity of dermatitis in patients receiving PMRT have not been well studied. Acute skin toxicities are generally more severe in the setting of PMRT than breast conservation therapy (BCT), as the skin itself is considered part of the radiation target with PMRT. There are remarkably little data available on the incidence of radiation dermatitis in the post-mastectomy chest wall setting. The three large randomized trials investigating the use of PMRT either do not report toxicity or report late toxicity excluding skin toxicities (Overgaard, Hansen et al. 1997; Overgaard, Jensen et al. 1999; Ragaz, Olivotto et al. 2005). One small retrospective series of 89 patients receiving PMRT using an electron technique reported that 19 patients developed dry desquamation, and only five developed moist desquamation (Hehr, Budach et al. 1999). In contrast, a series of 118 patients treated with a similar technique reported that 52% of patients developed grade 3-4 skin toxicity by Radiation Therapy Oncology Group (RTOG) criteria, and 31% of patients required an unplanned treatment break to recover from early radiation-induced skin toxicities (Spierer, Hong et al. 2004).

The development of normal tissue toxicities in breast cancer patients receiving adjuvant external beam RT demonstrates significant heterogeneity among individuals (Twardella, Popanda et al. 2003), which can be attributed to a variety of individual, tumor stage, cellular, and molecular factors. Increasing evidence suggests that individual genetic variations may also play a significant role in the development of adverse radiation responses (De Ruyck, Van Eijkeren et al.

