2005; Andreassen, Alsner et al. 2006; Alsbeih, El-Sebaie et al. 2007), but these remain poorly understood. Existing estimates on rates of radiation dermatitis are extrapolated from patients with intact breasts, who have been treated with a variety of techniques that affect the development of dermatitis. A randomized trial investigating the use of intensity-modulated RT (IMRT) in the setting of BCT demonstrated moist desquamation in 31.2% receiving IMRT and 47.8% with standard treatment, respectively (Pignol, Olivotto et al. 2008). The primary factor that predisposed to moist desquamation was large breast size; race-ethnicity and genetic factors were not assessed in this Canadian study. In Table 1, we summarize the results from the few studies that have specifically evaluated skin toxicities in breast cancer patients who have received PMRT.

Table 1. Incidence of RT-Related Adverse Reactions in PMRT Patients

Sample Size	Skin Toxicities	Study Variables	References
41 PMRT patients	Late tissue fibrosis and telangiectasias	XRCC1&3, TGFB1, SOD2, APEX SNPs	Andreassen et al., 2003
118 PMRT patients	52% grade 3-4 acute skin toxicity	-	Spierer et al., 2004
89 PMRT patients	19 dry desquamation; 5 moist desquamation	-	Hehr et al., 1999

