11.0 TOXICITIES/SIDE EFFECTS

The patient will be monitored for erythema and desquamation in the radiation field, which are expected side effects from chest wall radiotherapy. Some patients may develop moist desquamation, which usually heals within a few weeks and is treated with Silvadene cream and/or hydrocolloid dressings. Treatment breaks secondary to severe acute skin toxicities and/or cellulitis during radiation are not anticipated.

If a patient develops grade 2 or greater moist desquamation, or adverse reaction to the topical agent, she will be instructed to discontinue study cream and will receive standard of care management as determined by the patient's provider. These patients will continue to be evaluated according to study guidelines, and intervention will be noted on the Provider Skin Toxicity Assessment form. Patients who develop grade 2 erythema without the presence of moist desquamation will continue to use study cream without deviation from protocol guidelines.

Side effects from MF are uncommon. In controlled clinical studies of MF, the incidence of adverse reactions of burning, pruritus, and skin atrophy was 1.6%. Infrequent side effects include irritation, dryness, folliculitis, hypertrichosis, acneiform eruptions, hypopigmentation, allergic contact dermatitis, secondary infection, striae, and miliaria. Systemic absorption may produce reversible hypothalamic-pituitary-adrenal (HPA) axis suppression, manifestations of Cushing syndrome, hyperglycemia, and glycosuria.

Eucerin Original side effects are rare but include skin redness, irritation, and itching.

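### Does maximum toxicity need a between-arm test, and does the 52% benchmark undermine the 50% control rate?

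*Combined protocol and SAP*

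**What the plan says.** Section 2.0 lists as a secondary objective "To determine maximum reported skin toxicity and the time to occurrence". The neighbouring objective, on patient-reported symptoms, is worded as a comparison. Sections 12.1 and 12.2 have the maximal score and time to occurrence recorded weekly and at the two-week follow-up.

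Section 14.0 then assigns the analyses:

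- The primary test is a two-sided comparison of the proportions with grade ≥2 toxicity.
- Skindex-16 is compared by Wilcoxon tests, with an unnamed multiplicity adjustment.
- Time to occurrence is handled by Kaplan-Meier, log-rank and/or Cox methods, with tests where a comparison is needed.
- For maximum toxicity: "Maximum reported skin toxicities will be tabulated and summary statistics will be provided".

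On the control rate, Section 14.0 takes about 50% from the institution's radiation oncologists and adds: "This estimate is slightly lower than the findings from the" 118-patient electron-beam series. The reason it gives is that this trial also includes photon patients. Section 3.2 reports that series as "52% of patients developed grade 3-4 skin toxicity by Radiation Therapy Oncology Group (RTOG) criteria", and its Table 1 as "52% grade 3-4 acute skin toxicity". This trial grades by CTCAE 4.0.

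**The concern.** Two things look wrong.

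First, the maximum grade is collected on every patient but compared only through a cut at grade 2. If mometasone made reactions milder without bringing patients below grade 2, the primary test would reject in favour of mometasone only at its false-positive rate (about 0.026). A test chosen after seeing the table would be post hoc. Section 4.1 speaks of preventing moderate to severe dermatitis, so severity above the cut is not foreign to the trial.

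Second, a grade ≥2 rate cannot be lower than the grade 3-4 rate in the same patients. The 52% is therefore only a floor for grade ≥2 in that series, on another scale, and it cannot corroborate 50%. Other text seems to point to milder reactions: in an 89-patient series "19 patients developed dry desquamation, and only five developed moist desquamation", and Section 11.0 expects no breaks for severe skin toxicity, although in the 118-patient series "31% of patients required an unplanned treatment break". If the control rate were badly misjudged, the sample size could be too small.

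**Working it through.** **1. The plan's own power.** Inputs from Section 14.0: 62 per arm, 50% against 25%, looks at 31 and 62 per arm, thresholds p<0.005 and p<0.048.

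Single look at 0.048, pooled variance under the null:

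- s0 = √(2×0.375×0.625/62) = 0.0870
- s1 = √[(0.5×0.5 + 0.25×0.75)/62] = 0.0840
- power = Φ[(0.25 − 1.977×0.0870)/0.0840] = 0.824

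With both looks, the exact binomial calculation gives 0.835, and the normal-theory type I error is 0.0499. The stated 0.83 and 0.05 reproduce.

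**2. Does the loose benchmark matter?** The benchmark gives grade ≥2 of at least 52% in its own series, by an unknown margin. The milder evidence does no better. Moist desquamation in 5/89 = 5.6% is also only a floor for grade ≥2, because Section 3.4 counts moderate to brisk erythema as well. The expectation about breaks concerns severe toxicity, not the grade ≥2 rate. Power of the two-look design over assumed control rates is:

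| Control grade ≥2 | 25-point reduction | Rate halved | Odds ratio 1/3 |
|---|---|---|---|
| 30% | – | 0.52 | 0.67 |
| 40% | – | 0.69 | 0.78 |
| 50% | 0.83 | 0.835 | 0.835 |
| 60% | 0.81 | 0.93 | 0.86 |
| 70% | 0.82 | 0.98 | 0.86 |
| 80% | 0.86 | 0.998 | 0.795 |
| 90% | 0.93 | 1.00 | 0.60 |

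If the rate lies above 50%, the direction in which the benchmark points, power for the planned 25-point difference stays between 0.81 and 0.93. Power drops for a halved rate at 30-40% and for an odds ratio of 1/3 at 90%, but no passage shows either control rate.

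**3. What would a test of maximum grade add?** The candidate is a van Elteren test stratified by reconstruction and BMI. Assumptions: 62 per arm in strata of 16/16/15/15, 2% grade 0 in controls, a common odds ratio of 1/3, and Bonferroni over two Skindex-16 times plus maximum grade, so 0.05/3 = 0.0167.

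| Control grade ≥2 | Control grade ≥3 | Van Elteren, adjusted | Primary test |
|---|---|---|---|
| 50% | 10-30% | 0.73-0.74 | 0.835 |
| 70% | 20-30% | 0.79-0.80 | 0.86 |
| 80% | 20-40% | 0.75-0.81 | 0.795 |
| 90% | 20-40% | 0.65-0.76 | 0.60 |

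Without adjustment it has 0.86 at 50% control and 0.80-0.88 at 90%. After adjustment it is below the primary test at 50% and 70%, about level at 80%, and ahead only at 90%.

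**4. Does it detect the shift it is meant for?** Take grade ≥3 halved with grade ≥2 unchanged, and compare with a plain test of grade ≥3 proportions. For 20% against 10%:

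- s0 = √(2×0.15×0.85/62) = 0.0641
- s1 = √[(0.16 + 0.09)/62] = 0.0635
- power at 0.05 = Φ[(0.10 − 1.960×0.0641)/0.0635] = 0.34
- power at 0.0167 = Φ[(0.10 − 2.393×0.0641)/0.0635] = 0.20

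| Shift in grade ≥3 | Control grade ≥2 | Van Elteren, 0.05 / 0.0167 | Grade ≥3 proportions, 0.05 / 0.0167 |
|---|---|---|---|
| 20% to 10% | 50% | 0.075 / 0.03 | 0.34 / 0.20 |
| 40% to 20% | 90% | 0.52 / 0.35 | 0.69 / 0.52 |

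In the first row, the van Elteren test is close to its null rates of 0.025 and 0.008. The rank test is the weaker tool for this pattern, and neither test is well powered at this size once adjusted.

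**The case for a change.** The case for a change is that both edits are nearly free. One sentence would prespecify a comparison on data already collected, and deleting another would remove a statement that does not do what it claims. A table cannot substitute for a prespecified test, and the primary test cannot see a shift within grade ≥2.

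Part of this stands. The benchmark sentence compares unlike quantities, and Section 14.0 explains the gap by beam type alone. A pure grade 3-to-2 shift would appear only descriptively.

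The rest carries less weight. Maximum grade is not the only provider-graded outcome outside the primary test: Section 14.0 allows log-rank or Cox comparison of time to skin toxicity. That can show a delay even if most patients eventually reach grade 2, although on a grade ≥2 event it does not separate grade 3 from grade 2. The added test is not free either, because it takes significance level from the Skindex-16 comparison, which Section 2.0 does word as a comparison. Its result would also be harder to read. Under Section 11.0, study cream stops at grade 2 or greater moist desquamation and standard care follows. "These patients will continue to be evaluated according to study guidelines", so some higher grades would arise off cream. The power figures above ignore this.

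**Conclusion.** No change follows. Tabulating maximum grade fits an objective that asks to determine it, and the trial's stated question is prevention of grade ≥2. Adding a rank test is a matter of preference with a real cost. Adjusted, it has less power than the primary test at the plan's own 50% control rate (0.73-0.74 against 0.835), gains clearly only near 90%, and is nearly blind to a modest grade 3-to-2 shift at 50%. An analyst interested in severity can read the between-arm difference in grade ≥3 from the planned table and give it a confidence interval, with no claim on the significance level.

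The benchmark sentence is imprecise background. The 50% rests first on institutional estimates. No sample size, power or threshold is shown to be wrong, and deleting the sentence would leave the design, analysis and conclusions as they are.

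This rests on assumed grade distributions, stratum sizes, odds ratios and a three-test Bonferroni adjustment, because the plan names no procedure. The true control rate is not known from the documents. A rate well below 50% would lower power for a halved rate (0.69 at 40%, 0.52 at 30%), but that is ordinary planning uncertainty, which the benchmark sentence neither causes nor resolves.
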